### 4.1. Overview

The traditional method of defining gastroparesis relies on demonstration of delayed gastric emptying in a symptomatic patient who does not have an obstruction or ulcer explaining their symptoms. The gastric emptying test does not always correlate with symptoms. Nevertheless, this definition based on delayed gastric emptying has the advantage of widespread acceptance and ready availability in the community and will provide a more uniform group of patients.

This study will enroll patients with gastroparesis and delayed gastric emptying. These patients can have either diabetic, idiopathic, or post-Nissen fundoplication gastroparesis. In addition, patients with symptoms similar to gastroparesis, but with normal gastric emptying will be enrolled as a reference group.

**Overlap with other functional dyspepsia:** The most frequently reported symptoms of gastroparesis include nausea, vomiting, early satiety, and postprandial fullness. Abdominal discomfort and pain also are noted by many affected patients and represent challenging symptoms to treat. There is some overlap between gastroparesis and functional dyspepsia as both symptoms and gastric emptying test results may meet definitions for both in a subset of patients. As a consequence, some patients with mild abdominal pain, nausea, vomiting, and evidence of delayed emptying are considered to have functional dyspepsia by some clinicians and gastroparesis by others. Patients with marked delay in gastric emptying should be diagnosed with gastroparesis and not functional dyspepsia. In general, predominant abdominal pain with lesser degrees of nausea is more consistent with a diagnosis of functional dyspepsia, whereas predominant nausea and vomiting with lesser degrees of abdominal pain is more characteristic of gastroparesis. Under the new Rome III criteria, nausea is not a diagnostic criterion for functional dyspepsia and so for the purposes of the Gastroparesis Registry 2, any patient with nausea (regardless of the degree of other dyspeptic symptoms) who has delayed gastric emptying will be classified as gastroparesis.

### 4.2. Symptoms of gastroparesis

#### 4.2.1. Gastroparesis with delayed emptying:

In the Gastroparesis Registry 2, the case definition for gastroparesis will require the following:

- Symptoms of nausea, vomiting, abdominal pain, bloating, and/or early satiety for at least 12 weeks (not necessarily contiguous)
- Scintigraphic evidence of delayed gastric emptying (using a standardized low fat Egg Beaters® meal defined as greater than 60% retention at 2 hours and/or greater than 10% retention at 4 hours)
- Exclusion of other causes of symptoms such as mechanical obstruction, inflammatory, or other structural lesions of the GI tract or non-gastrointestinal causes

This case definition for gastroparesis will provide a uniform group of patients for study for the GpCRC. GpR 2 will enroll patients with gastroparesis and defined as above with the following diagnostic categories: Diabetic, Idiopathic, and Post-Nissen fundoplication

#### 4.2.2. Symptomatic nausea and vomiting without delayed gastric emptying

Patients will qualify for enrollment in this category if they meet the criteria for gastroparesis defined for the protocol with the exception of a normal scintigraphic gastric emptying and no other

cause found. Many patients present with symptoms similar to those of gastroparesis but exhibit normal scintigraphic gastric emptying of a solid meal. Many of these individuals satisfy the Rome III definitions of chronic idiopathic nausea or functional vomiting.

#### **4.3 Target composition**

Patients will be recruited predominantly from outpatient clinics either in gastroenterology, diabetes, or primary care settings. Inpatients (patients in the hospital) with the diagnosis of gastroparesis will also be invited to participate.

In GpR 2, we will cap the number of the patients with symptomatic nausea and vomiting with normal gastric emptying (as described in section 4.2 above) to 20% of the total patients enrolled. In the GpR 2, patients with prior Nissen fundoplication will be eligible for enrollment and we will cap the patients with post-Nissen gastroparesis to 20% of the patients with delayed gastric emptying. Assuming the goal of 500 patients are entered into GpR 2 and assuming similar types of enrollment as in the first registry this will result in the following types of patients: 200 idiopathic gastroparesis patients, 50 idiopathic patients with normal gastric emptying, 120 with diabetic gastroparesis, 30 diabetic patients with normal gastric emptying, 80 post-Nissen gastroparesis patients, and 20 post-Nissen patients with normal gastric emptying.

---

## Gastroparesis Registry 2 Protocol

### 5. Eligibility criteria

---

#### 5.1. Inclusion criteria

- Symptoms of gastroparesis of at least 12 weeks duration (do not have to be contiguous) with varying degrees of nausea, vomiting, early satiety, post-prandial fullness, and/or abdominal pain
- An etiology of either diabetic, idiopathic, or post-Nissen fundoplication gastroparesis
- Gastric emptying scintigraphy of solids and liquids test using 4 hours Egg Beaters® protocol within the last 6 months with either:
  - Abnormal gastric emptying rate defined as an abnormal 2 hour (>60% retention) and/or 4 hour (>10% retention) result based on a 4-hour scintigraphic low fat Egg Beaters® gastric emptying study performed at a GpCRC clinical center.
  - Patients with a normal gastric emptying rate but with symptoms of gastroparesis may be enrolled and classified as possible gastroparesis or gastroparesis-like with normal gastric emptying
- Age at least 18 years at initial screening visit

#### 5.2. Exclusion criteria

- Inability to comply with or complete the gastric emptying scintigraphy test (including allergy to eggs)
- Presence of other conditions that could explain the patient's symptoms:
  - Pyloric or intestinal obstruction as determined by endoscopy, upper GI series or abdominal CT scan
  - Active inflammatory bowel disease
  - Known eosinophilic gastroenteritis
  - Primary neurological conditions that could cause nausea and/or vomiting such as increased intracranial pressure, space occupying or inflammatory/infectious lesions
  - Acute liver failure
  - Advanced liver disease (Child's B or C; a Child-Pugh-Turcotte (CPT) score of  $\geq 7$ )
  - Acute renal failure
  - Chronic renal failure (serum creatinine  $>3$  mg/dL) and/or on hemodialysis or peritoneal dialysis
- Total or subtotal (near complete) gastric resection, esophagogastrostomy, gastrojejunostomy, or gastric bypass. Note: patients with prior fundoplication will be eligible for enrollment.
- Any other plausible structural or metabolic cause
- Any other condition, which in the opinion of the investigator would interfere with study requirements
- Inability to obtain informed consent

Clinical centers must be certified by the Scientific Data Research Center to start enrollment in the Gastroparesis Registry 2. Prior to implementation of this protocol, the principal investigator must have the protocol and consent form approved by the Institutional Review Board for Human Research (IRB) at his/her institution. Once a candidate for GpR 2 has been identified, study related details will be carefully discussed with the patient including the follow-up visit schedule and procedures. The patient will be asked to read and sign the consent form that was approved by the IRB. There will be a separate consent for the collection, storage, and use of DNA for genetic research.

---

## Gastroparesis Registry 2 Protocol

### 6. Schedule of visits and procedures

---

#### 6.1. Overview

Patients will have a scintigraphic gastric emptying test of both solids and liquids for their clinical evaluation of gastroparesis. To rule out other disorders, patients must have had an upper endoscopy within 2 years prior to registration. Information will be collected during screening using 1) medical history and physical examination; 2) validated questionnaires; 3) laboratory studies; and 4) gastric emptying test. In addition, tests investigating the pathophysiology will include ingesting a wireless motility capsule to assess whole gut transit, autonomic function testing, electrogastrography to assess for gastric dysrhythmias, water load testing to assess for gastric accommodation. Plasma and serum samples will be saved on each patient. Patients will then be followed over time, being seen every 24 weeks, collecting information on 1) treatments being used, 2) change in medical condition; and 3) validated questionnaires assessing symptoms, abdominal pain, and quality of life. A follow-up gastric emptying test will be obtained at the 48 week visit. Plasma and serum samples will be collected from each patient on a yearly basis.

#### 6.2. Patient selection, screening and enrollment visits

Many of the Gastroparesis Registry 2 (GpR 2) patients will likely come from the first Gastroparesis Registry, the current patient rosters of the GpCRC investigators, and new patients referred to them for evaluation and treatment of gastroparesis. Patients who are thought to be eligible will be invited to screen for enrollment in the GpR 2. Patients may be referred from physicians outside the Consortium and some patients may refer themselves to be included in the GpR 2. Patients considered by the clinical center investigator as likely to be eligible for enrollment in the GpR 2 may be consented and screened at a visit that is part of the ongoing clinical care of the patient. Tests may be ordered and billed to insurance to appropriately complete the evaluation of the disease and general medical condition according to reasonable standard of care.

Consent for screening and HIPAA authorization to disclose protected health information with the GpR 2 must be obtained from the patient prior to initiating data collection for the GpR 2; this consent and authorization must be obtained at the start of the initial screening visit. At the initial screening visit, the details of GpR 2 participation will be introduced. If the patient consents and is judged to have definite or possible gastroparesis, then he/she may enter the formal screening phase. Screening will include both prospective and retrospective data collection. Prospective data collection will be carried out by completion of forms and questionnaires by patients and by performance of various laboratory tests and clinical procedures on patients. Retrospective data collection will be carried out by review of the patient's medical chart and abstraction of various data elements. Abstracted data may include laboratory and radiology test results within defined time windows. The screening visits may occur on separate calendar days and may take place over several visits occurring over a period of up to 16 weeks after registering the patient for study screening.

The maximum follow-up on a patient enrolled into the GpR 2 will be approximately 5 years. Data will be collected during screening visits to establish baseline values, and then every 24 weeks after enrollment. If the patient returns in the interim for exacerbation of gastroparesis symptoms, an interim visit will be keyed in the database to reflect the exacerbation of symptoms. [Appendix 11.2](#) summarizes the data collection schedule for screening, enrollment, and follow-up visits.

The purpose of the screening visits is to collect data needed to determine eligibility and establish baseline values. Activities at screening visits include:

- Reviewing and signing the Gastroparesis Registry 2 informed consent
- Reviewing and signing the Gastroparesis Registry 2 HIPAA authorization form
- Assignment of GpCRC patient identification number (if patient is new to the GpCRC)
- Detailed medical/medication history
- Physical examination including vital signs, height, weight, and anthropometric measurements
- Review status of laboratory tests, including those reflecting glycemic control
- Review status of gastrointestinal tests including endoscopy
- Review status of gastric emptying scintigraphy
- If needed, patient to sign medical records release to obtain prior reports
- Patient to provide location/contact information
- Obtain retrospective health history information/materials relevant to study eligibility
- Clinical center coordinator to register patient on clinic data system
- If needed, clinical center coordinator to request prior reports from health care provider
- Perform electrogastrogram (EGG) with caloric meal and wireless motility capsule test
- Perform autonomic function testing
- Perform EGG with water load test
- Questionnaires to be filled out by the patients
  - Patient Assessment of Upper Gastrointestinal Disorders Symptom Severity Index (PAGI-SYM)
  - Patient Assessment of Upper Gastrointestinal Disorders - Quality of Life (PAGI-QOL)
  - Health related quality of life (SF-36v2)
  - Beck Depression Inventory (BDI-II)
  - State Trait Anxiety Inventory (STAI)
  - Patient Health Questionnaire (PHQ-15)
  - Neuropathy Total Symptom Score (NTSS-6)
  - Rome III Diagnostic Questionnaire for Adult Functional GI Disorders
  - Brief Pain Inventory
  - Block 2005 Food Frequency Questionnaire
  - Block Energy Expenditure Survey
  - Nausea Profile and Vomiting questionnaire
  - GpCRC abdominal pain questionnaire

During the screening visits, the patient completes the questionnaires needed for enrollment in the Gastroparesis Registry 2 and has blood drawn for standard of care laboratory tests and specimen (plasma, serum, and DNA) banking. The patient must attend the screening visits after an overnight fast of at least 8 hours and will be instructed to bring a snack to be eaten after fasting blood is drawn. Review patient chart for standard of care baseline laboratory data required (see [Appendix 11.3](#)):

- Complete blood count (white blood cell count (WBC), red blood cell count (RBC), hemoglobin, hematocrit, platelet count)
- Comprehensive metabolic panel (sodium, potassium, chloride, carbon dioxide, calcium, BUN, creatinine, glucose, and liver panel including total protein albumin, total bilirubin, aspartate aminotransferase (AST), alanine aminotransferase (ALT), alkaline phosphatase)
- Thyroid stimulating hormone (TSH)
- Erythrocyte sedimentation rate (ESR), high sensitivity C-reactive protein (hs-CRP), antinuclear antibody (ANA)
- Vitamin B12, 25-hydroxy vitamin D level
- Hemoglobin A1c
- Lipid panel (total cholesterol, LDL, HDL, triglycerides)

Tests must have been done within 16 weeks prior to registration, except ANA which may have been done in last year. Other procedures during screening visits include:

- Fasting blood collection for plasma and serum banking
- Blood collection for DNA banking (no fasting required)

**Gastric emptying scintigraphy:** To establish a diagnosis of definite gastroparesis (see section [4.1](#) for definition), the patient must have a 4 hour scintigraphic evaluation of gastric emptying of solids and liquids using a standardized low fat Egg Beaters® meal with an accompanying PAGI-SYM completed at a GpCRC center in last 6 months (schedule as needed) and available for review. Since the patients are symptomatic from a possible gastric motility disorder, the gastric emptying of solids and liquids scintigraphy test is being performed for the patients' clinical evaluation. The GpCRC investigator must confirm that the patient meets the criteria for definite gastroparesis. The gastric emptying scintigraphy may have been obtained within 6 months prior to registration. Medications that delay gastric emptying such as narcotic analgesics and medications that enhance gastric emptying such as prokinetics will be stopped 3 days prior to the gastric emptying test. Medications taken during the past week will be recorded. For diabetic patients, a fasting blood glucose level must be checked prior to the gastric emptying test to ensure it is less than 270 mg/dL. Patients will also complete the PAGI-SYM form immediately prior to the gastric emptying test.

The gastric emptying tests will be performed at the GpCRC clinical centers. The clinical centers will save each scintigraphy test and send the de-identified images to [name] at Temple University Nuclear Medicine for central analysis of regional gastric emptying.

**Screening visit 2:** Patients must discontinue use of proton pump inhibitors for 7 days, and stop histamine 2 antagonists, prokinetics, narcotics, anticholinergics, and cannabinoids for 3 days prior to this visit. If the patient normally takes insulin, they will be asked to take only half of their normal long-acting insulin. Record fasting glucose for diabetic patients; the blood glucose level must be checked to ensure it is less than 270 mg/dL to continue with the test. Patients will come to the center after fasting and will have a baseline electrogastrogram (EGG). Then they will eat a nutrient bar (SmartBar®) with water and swallow a wireless motility capsule (SmartPill®) with additional water, followed by a 90 minute EGG recording. Patients will continue to abstain from prokinetics, proton pump inhibitors, 'over the counter' laxatives, isotonic PEG electrolyte preparations (e.g. MiraLax), and prescription laxatives (e.g. lubiprostone) after ingesting the SmartPill® until they return for the follow-up visit in 4-7 days. These tests are described in detail in section [6.7.3](#). (All details of the EGG recording procedure, wireless motility capsule test, and specific questionnaires will be in the Standard Operating Procedures (SOP) manual.)

**Screening visit 3 (4-7 days after visit 2):** Record fasting glucose for diabetic patients; the blood glucose level must be checked to ensure it is less than 270 mg/dL to continue with the test. If the patient's blood glucose level is greater than 270 mg/dL, the EGG and water load test must be rescheduled for another day.

The study physician or coordinator will collect the SmartPill® receiver and download the data, and then the patient will undergo autonomic function testing to evaluate heart rate variability (see section [6.7.4](#)). Next the patient will have a 15 minute baseline electrogastrogram (EGG) and then complete a water load test, followed by a 30 minute EGG recording (this test is described in section [6.7.5](#)). Patients will have blood drawn for DNA and serum/plasma banking as the last procedure for the visit.

**Enrollment:** The GpR 2 data system will include software to check patient eligibility based on keyed

data forms. The eligibility check task may be run at any time, and there is no limit on the number of times it may be run. The output from the task will list the eligibility checks that the patient has failed and a summary finding that the patient is eligible or ineligible for enrollment into the study. Thus staff can use this task to identify the items that still need to be completed, keyed, or verified after data from screening visits are keyed. The date of enrollment is the time zero for reckoning all follow-up visits (i.e., all follow-up visits are scheduled at specific times measured from the date of enrollment). On the day of enrollment the data system will generate a visit windows schedule for the patient; this schedule will indicate the ideal date for each follow-up visit, as well as the time window around the ideal date during which the follow-up visit may be done and the data collected at the visit may be used in the study.

*Note: Some patients may not be able complete all the study procedures. For instance, some may not have the liquid phase gastric emptying scintigraphy performed due to center specific logistical issues or some may not be able to swallow the SmartPill® or some may not complete EGG with SmartBar or water load testing. These patients may still be enrolled.*

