***Patient preparation required for the SmartPill® with EGG test***

- 1) Patient will stop proton pump inhibitors for 7 days prior to visit 2;
- 2) Patient will stop histamine 2 antagonists, prokinetics, narcotics, anticholinergics, constipation medications (over the counter laxatives, isotonic polyethylene glycol (PEG) electrolyte preparations (e.g. MiraLax), and prescription laxatives (e.g. lubiprostone), and cannabinoids for 3 days prior to the visit; and
- 3) Patients will continue to abstain from prokinetics, proton pump inhibitors, and ‘over the counter’ laxatives, isotonic PEG electrolyte preparations (e.g. MiraLax), and prescription laxatives (e.g. lubiprostone) after ingesting the SmartPill® until they return for the follow-up visit in 4-7 days.
- 4) Patients will not swallow the SmartPill®, if they have a history of bezoars (retained liquid or poorly organized solids are permitted), significant dysphagia, prior gut lumen surgery (except fundoplication), known strictures, prior inflammatory bowel disease, and cardiac medical devices (gastric stimulators, insulin pumps, continuous glucose monitors are permitted).

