After the baseline EGG recording is completed, the patient will begin the standard solid meal test by sitting up in the chair and ingesting one SmartBar® in a 10 minute period with 50 mL of room temperature water. It is expected that 100% of the bar will be ingested. The percentage of the SmartBar® that is consumed will be documented. After the SmartBar® is consumed; the SmartPill® will be ingested with another 50 ml of water and another visual analog scales symptoms sheet will be completed. The subject will then recline in the 30-45 degree position that they were in for the fasting baseline condition. The electrodes will be checked to verify that they are well adhered to the skin and the respiratory belt will be checked to verify it is snug before starting the EGG recording for the 90 minute postprandial period. Visual analog scales for stomach fullness, hunger, nausea, bloating, and abdominal discomfort will be completed at the 10, 20, 30, 60, and 90 minute time periods after ingestion of the SmartPill®. The patient may get out of the chair to stretch for 2 minutes at 30 and 60 minutes if necessary. At the 90 minute point the test is completed and the electrodes are removed. (Further details of the EGG recording and questionnaires will be in the SOP.)

Patients will be permitted to leave the study center after completion of the 90 minute EGG recording after SmartPill® ingestion. Study participants will leave with instructions to:

- 1) Remain fasting for 6 hours after SmartPill® ingestion; thereafter resume a normal diet; maintain a diary recording times of meal ingestion, bowel movements, and sleep; and keep the receiver in close proximity for 4-7 days. An event marker on the receiver will be depressed for diary entries.
- 2) Complete all remaining questionnaires for GpR 2: food questionnaire, nausea and vomiting questionnaire, neuropathy profile; abdominal pain questionnaire, state trait anxiety
- 3) Continue to abstain from prokinetics, proton pump inhibitors, and 'over the counter' laxatives, isotonic PEG electrolyte preparations (e.g. MiraLax), and prescription laxatives (e.g. lubiprostone) after ingesting the SmartPill® until they return for the follow-up visit
- 4) Return fasting for a follow-up visit 4-7 days after SmartPill® ingestion to return the receiver, questionnaires, and diaries for analysis.

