#### *SmartPill® transit and contractile parameters collected*

Gastric emptying will be calculated from time of ingestion to the time the capsule passes to the duodenum as defined by abrupt  $>2$  pH unit increases from the lowest postprandial value to  $>4$  that do not decrease to  $<4$  for  $>10$  minutes. Gastric emptying  $>5$  hr is considered delayed. Ileocecal passage

is defined when >1 pH unit decreases occur >30 min after gastric emptying; such pH decreases are noted in >95% of cases. Small bowel transit will be calculated from times of duodenal to ileocecal passage. Small bowel transit >6 hours is considered delayed. Anal expulsion is determined by 0.045°F/second temperature decreases. Colon transit will be calculated from times of ileocecal passage to anal expulsion. Colon transit >59 hours is considered delayed. Two pressure parameters will be computer calculated (MotilitGI, GIMS Data Viewer, SmartPill Corp., Buffalo, NY). Numbers of contractions >25 mmHg will be standardized to activity per 15 min to compare gastric, small bowel, and colon recordings of different length. Summed contractility measures >25 mmHg per 15 minutes will be provided by motility indices calculated as log (mmHg x min). Numbers of gastric contractions <29 and motility indices <9.82 in the hour before gastric emptying are considered abnormal.

Symptom profiles in those with isolated delayed gastric, small bowel, and colon transit as well as with generalized transit delays in >2 gut regions, and normal transit throughout. Symptoms will be compared in those with increased vs. normal vs. decreased contractile parameters in the same subsets. These studies will provide detailed characterizations of diffuse and generalized gut transit and contractile abnormalities in patients presenting with symptoms of gastroparesis.

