**Stopping medications for gastroparesis:** For participation in this study, prescribed medications may need to be stopped temporarily for the testing required for the study: gastric emptying tests, wireless motility capsule, and electrogastronomy. These medications include those that speed up stomach emptying. Medicines like this include metoclopramide (Reglan), erythromycin, and domperidone (Motilium). Medications that slow down the movement through the GI tract include anticholinergic agents such as Levsin and NuLev and pain medications such as Percocet, Tylenol #3, Vicodan, Dilaudid, Fentanyl patch, and others. If patients are taking any of these medications and they are helping their symptoms, if they are stopped, their symptoms may return or worsen. The stopping of medications is for a short time only (1 week) and is not felt to cause any undue hardship on the patient.

**Safety issues related to patient privacy:** There is a potential risk to patient privacy. Every effort will be made to maintain patient's privacy. It is the investigator's responsibility to conduct the protocol under the current version of Declaration of Helsinki, Good Clinical Practice, and rules of local IRBs. The investigator must ensure that the patient's anonymity is maintained in their data submission to the Scientific Data Research Center. Patients will be identified only by an identification code but not by their name, SSN, or hospital medical record number. Investigators will maintain a separate confidential enrollment log which matches identifying codes with the patients' names and addresses (i.e., available only to local clinic staff). All study material will be maintained in strict confidence.

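### The post-ingestion capsule drug lists omit narcotics, anticholinergics, cannabinoids and H2 antagonists, so drugs stopped beforehand may be restarted while small-bowel and colon transit are recorded

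*Protocol*

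**What the plan says.** Section 6.2 (Screening visit 2) requires a 7-day stop of proton pump inhibitors and tells patients to "stop histamine 2 antagonists, prokinetics, narcotics, anticholinergics, and cannabinoids for 3 days prior to this visit". Section 6.7.3 repeats this in its test criteria and in its patient preparation list, which adds constipation drugs.

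For the period from ingestion to the return visit at 4 to 7 days there are three lists:

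- Section 6.2, Screening visit 2: "Patients will continue to abstain from prokinetics, proton pump inhibitors", followed by laxatives.
- Section 6.7.3, patient preparation, item 3: "Patients will continue to abstain from prokinetics, proton pump inhibitors, and" laxatives.
- Section 6.7.3, test protocol, take-home item 3: "Continue to abstain from prokinetics, proton pump inhibitors, and" laxatives.

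The take-home instructions also tell the patient to fast for 6 hours after ingestion and to "maintain a diary recording times of meal ingestion, bowel movements, and sleep". Drugs are not among the diary items.

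Transit is read after ingestion. Gastric emptying is delayed beyond 5 hours, "Small bowel transit >6 hours is considered delayed", and colon transit is delayed beyond 59 hours. The test is done at baseline only (Design synopsis; Section 11.2). Section 9.1 states: "Medications that slow down the movement through the GI tract include anticholinergic agents", and goes on to list opioid pain drugs. It gives the length of stopping as one week, without tying that to a drug class or to the time after ingestion.

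**The concern.** A 3-day stop that ends at ingestion suits a test that is over within hours. Small-bowel and colon transit run for days after the capsule is swallowed. Of the drugs that affect motility, the post-ingestion list holds back prokinetics and laxatives, but not the two groups that the protocol itself describes as slowing the gut. A centre that follows all three lists exactly could let a patient resume an opioid on leaving the clinic and then record the slowed transit as dysmotility.

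The readings feed the expectations in Section 3.2.3 (small-intestinal delay in 20%, colon delay in 50%), the comparisons of symptoms by transit, and the hypothesis that intestinal dysmotility worsens prognosis. Section 2.1 links narcotic dependence to pain in the more severe cases. Drug-induced delay would therefore probably gather in sicker patients and could distort those associations as well as the rates. The test is not repeated, so a later reading cannot correct the first.

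**Working it through.** **Step 1: compare the lists.**

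| Class | Before ingestion | Ingestion to return visit |
|---|---|---|
| Proton pump inhibitors | 7 days | barred |
| Prokinetics | 3 days | barred |
| Laxatives | 3 days (Section 6.7.3 preparation list) | barred |
| Narcotics | 3 days | not named |
| Anticholinergics | 3 days | not named |
| Cannabinoids | 3 days | not named |
| H2 antagonists | 3 days | not named |

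All three post-ingestion lists have the same content.

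**Step 2: time exposed.** Inputs are the cut-offs in Section 6.7.3 (5, 6 and 59 h), the 6 h fast and the 90-minute EGG.

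- Transit at the cut-offs: 5 + 6 + 59 = 70 h.
- If the fast is taken to exclude oral drugs: 70 − 6 = 64 h open, 64/70 = 91%.
- From leaving the centre: 70 − 1.5 = 68.5 h open, 68.5/70 = 98%.
- The named classes are barred for 4 × 24 = 96 h to 7 × 24 = 168 h.

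By segment, with the fast excluded, the stomach (0 to 5 h) is not exposed, the small bowel (5 to 11 h) is exposed for 11 − 6 = 5 h, and the colon (11 to 70 h) for all 59 h. The colon makes up 59/64 = 92% of the exposed time. For a 6 h small-bowel transit after gastric exit at g hours, the exposed part is min(6, g) hours: short in a patient who empties early, complete once g reaches 6. The protocol does not say that the fast excludes drugs, and Section 9.1 names a fentanyl patch, which a fast would not stop.

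**Step 3: direction.** For anticholinergics and opioids, Section 9.1 gives it: slower movement, hence more apparent delay. The protocol states no direction for cannabinoids and no transit effect for H2 antagonists. The latter matter because gastric exit is read from a pH rise, the proton pump inhibitors are held, and H2 antagonists are released.

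**Step 4: can the size be found?** If a share u of patients restart, a share m of otherwise normal restarters cross a cut-off, and p is the drug-free rate of delay, the added delay is u × m × (1 − p). The protocol gives p only as an expectation and gives neither u nor m. Under assumed values:

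- u = 0.05, m = 0.10: small bowel 0.05 × 0.10 × 0.80 = 0.4 points; colon 0.05 × 0.10 × 0.50 = 0.25 points.
- u = 0.40, m = 0.50: small bowel 0.40 × 0.50 × 0.80 = 16 points; colon 0.40 × 0.50 × 0.50 = 10 points.

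Standard errors at n = 500 are √(0.2 × 0.8/500) = 1.8 points and √(0.5 × 0.5/500) = 2.2 points, larger if fewer take the capsule. The assumed range runs from well below one standard error to several, so it does not settle the size. Using one m for both segments is itself unsupported, given the unequal exposure in Step 2.

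**The case against.** **Permission is inferred from silence.** No sentence says these drugs may restart, and Section 6.2 sends the details of the capsule test to an SOP that is not available here. The SOP may close the gap. That limits the point to what the protocol instructs, but the protocol does name drug classes for the post-ingestion period, three times, and a centre can reasonably treat the unnamed ones as released.

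**The one week in Section 9.1 may mean a full hold.** Three days before plus the 4-day minimum after makes 7 days, and the passage covers anticholinergics and pain drugs. This reading is possible, so the sentence is ambiguous and should not be counted as a second, separate error. It is general risk text, however, and sets no rule for the time after ingestion.

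**Users can already be identified.** Section 6.4 captures all prescription drugs in the 6 months before registration, pain drugs included. This stands in part: results can be reported with and without prior users. Prior use is not use during recording, though. A prior user who stayed off the drug would be counted as exposed.

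**The choice may be deliberate.** Section 6.7.3 asks only that patients be able to stop narcotics for 3 days, and a longer hold could deter dependent patients. The protocol gives no such reason, but the burden is real and the remedy must allow for it.

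**The largest effect is claimed where exposure is shortest.** A reader might take the 16-point small-bowel figure as an estimate. It is not one: it rests on assumed inputs, and small-bowel exposure may be brief if the fast excludes oral drugs.

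**Conclusion.** The omission is real and consistent across all three post-ingestion lists. As written, narcotics, anticholinergics, cannabinoids and H2 antagonists may be restarted while small-bowel and, above all, colon transit is recorded, and the diary would not show it. For narcotics and anticholinergics the bias is toward more apparent delay. That it falls more on sicker patients is probable from Section 2.1, but not demonstrated.

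Its size cannot be computed from the protocol. What can be stated is the exposure: 64 to 68.5 of 70 hours at the cut-offs, most of it colon. A reader might infer that the protocol authorises a restart, or that the capsule results will be invalid. Neither follows: the permission comes by omission, an SOP may narrow it, and how many patients restart is unknown. The point concerns one baseline test among many in the registry, which patients may miss and still enrol (Section 6.2). It is worth correcting because the correction is cheap and the test is not repeated.

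**What to change.** 1. Add narcotics, anticholinergics and cannabinoids to the post-ingestion list in Section 6.2 (Screening visit 2) and in Section 6.7.3 (patient preparation item 3; take-home item 3), until capsule expulsion or visit 3. Add H2 antagonists for consistency with proton pump inhibitors.
2. Where narcotics cannot be withheld that long, allow the restart, record drug, date and time in the existing diary, and report small-bowel and colon transit with and without exposed patients.
3. Align the one week in Section 9.1 with the resulting stop. Held to visit 3, classes stopped 3 days before run 3 + (4 to 7) = 7 to 10 days, and proton pump inhibitors 7 + (4 to 7) = 11 to 14 days.

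The cost is one phrase in three places, one diary column and one corrected duration, with no added visit or test. Some patients abstain for longer; the record-and-report option eases this for those who depend on narcotics.
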